***Note on primary outcome time frame**

Our original outreach timeline was to send a letter on the first day of the study, a patient portal message 2 weeks later, an SMS 2 weeks after that (4 weeks after the letter), and measure the primary outcome 2 weeks after the final message. Therefore, we had planned to measure the primary outcome 6 weeks after the study start date, with 2 weeks between the final message and primary outcome measurement.

However, due to administrative and technical delays outside our control, patient portal messages were sent 18 days after the letters, and SMS messages were sent on 3 separate days - 15 days, 24 days, or 25 days after the patient portal messages. Given deviations from

our planned pacing, we changed the primary outcome time frame to 2 weeks following the final outreach date, which is 11/5/21, 8 weeks + 1 day after the study start date.

Corrections for multiple comparisons

For questions 1-3, we provided clear, independent hypotheses above. We will not correct for multiple comparisons in these analyses, as adjustment is not appropriate for individual testing, where each result must be statistically significant to reject its associated individual null hypothesis (Rubin, 2021). That is, each significant result is an indicator of a specific null hypothesis rejection and has no direct bearing on the success of other hypotheses or the overall study.

Because the analysis proposed to address question 4 is exploratory and involves 3 separate pairwise comparisons against the joint null hypothesis that there is no significant difference across the groups, reported p-values will be adjusted for family-wise error rate across the three comparisons using Tukey's HSD.

Sensitivity analyses and robustness checks

Some patients lived at the same address, but we decided to randomize patients independently, without accounting for whether a household member was also in the study. Therefore, some patients may have been assigned to different groups from their household members. Alternatively, it is possible household members were assigned to the same group. Either possibility may affect the impact of our intervention (e.g., the same messages received by multiple household members may reinforce the message and strengthen the impact of the messages, while different messages could cause confusion and weaken the messages' effectiveness). To ensure findings do not depend on such interactions between patients residing at the same address, we will run a sensitivity analysis by removing all patients who share an address with another patient in the study and computing the same analyses listed above.

Recent work suggests that OLS regressions are appropriate in randomized experiments with binary outcome variables such as ours (Gomilla, 2021). However, as a robustness check, we will also run the regressions described above as logistic regressions instead of OLS regressions.

Additionally, we plan to exclude some patients from our primary analyses, as noted below in "Analysis exclusion criteria." We will run an intent-to-treat analysis as a robustness check, including all patients who passed away during our study, those who were inadvertently sent protective risk reasons, and those who were vaccinated prior to the study beginning. We will however exclude from all analyses all patients who passed away prior to our study start date (9/9/21), and those inadvertently included despite not satisfying all of the inclusion criteria. A small group of patients did not have a valid mailing address in their medical records, or their print letters were returned to sender. Our subsequent myGeisinger messages referred patients to the letter that was sent. To avoid confusion, we did not send myGeisinger or SMS messages to patients who were never sent a letter, or whose mail was returned prior to these modality send dates. We do not exclude these patients because this would differentially exclude subjects

across the arms. We will note the small fraction of the treatment arms that were not treated for this reason.

We will also rerun the OLS regression analyses including a binary covariate for whether each patient has an assigned Primary Care Provider (PCP) who works at Geisinger, as flu shot data in the Geisinger EHR may be less reliable from those with an external PCP.

Finally, as an additional robustness check, we will run OLS regression analyses controlling for sex, 10-year age bins, and interactions among sex and age as covariates.

Secondary outcomes

We will use the approaches described in analyses 1-4 above to evaluate the impact of the intervention on the secondary outcome measures listed in the pre-registration:

1. Flu vaccination at 9 weeks after the final outreach date [Time Frame: Within 9 weeks of the final outreach date, within 15 weeks + 1 day of the study start] *

Received a flu vaccination

2. Flu diagnosis [Time Frame: 8 months (between September 9, 2021 and April 30, 2022)]

Received a "high confidence flu" diagnosis (with positive polymerase chain reaction [PCR]/antigen/molecular test) and/or "likely flu" diagnosis (as assessed via International Classification of Disease [ICD] codes or Tamiflu administration or positive PCR/antigen/molecular test)

3. Flu complications [Time Frame: 11 months (between September 9, 2021 and July 31, 2022)]

Diagnosed with flu-related complications

4. Healthcare utilization [Time Frame: 11 months (between September 9, 2021 and July 31, 2022)]

Visited ER, was hospitalized, or had flu-related insurance claims

*Because our outreach timeline was delayed (see above), we will delay the time frame for Secondary Outcome 1 from 3 months following the study start to 9 weeks following the final outreach date.

Additional exploratory analyses

1. Number of reasons

Patients in groups 4 and 5 were randomized to receive either 1 or 3 of the top reasons why they were considered high risk for flu. We will run an OLS regression testing for main effects and interactions between the number of reasons (1 reason, 3 reasons) and message type (group 4: medical records message, group 5: algorithm message) on flu vaccination.

2. Age

While older patients tend to be aware of their increased vulnerability, younger patients may be more surprised to learn of their high-risk status. We will therefore examine the differential response of patients 65 or above vs. below age 65 by introducing this age variable as a moderator and assessing if it interacts with experimental group to affect vaccination behavior. We will also conduct this analysis using age as a continuous variable.

3. Modality

Patients who received intervention messages (groups 2, 3, 4, and 5) may have received communications via up to 3 modalities. We will employ OLS regression to evaluate the impact of modality on outcomes of interest, assessing pairwise comparisons of the following modality combinations: letter only, letter + myGeisinger, letter + SMS, or letter + myGeisinger + SMS. Note that the number of modalities was not randomly assigned, but determined by patient preferences and data availability in the EHR, so these are observational analyses only.

4. Timing of shot

We will investigate whether the intervention messages influenced the timing (time elapsed since the beginning of the intervention, September 9, 2021) of flu shots. We will do this nonparametrically by graphing the rate at which subjects get a vaccination against time since the intervention began, separately by arm. We will employ regression analyses to test whether timing was differentially affected as well.

5. Timing of SMS

This analysis will focus on the subgroup of patients who were sent SMS messages. As mentioned previously, due to delays outside our control, SMS messages were sent on 3 separate days - 15 days, 24 days, or 25 days after patient portal messages. We will test whether there was a difference in flu shot uptake or timing in those who received earlier messages (15 days following the portal message) compared to those who received later messages (24 or 25 days after the portal message).

To this end, we will run the following analyses: (1) a linear regression testing for effects of message timing (early or late), message type (group 2, 3, 4 or 5), or their interaction, on flu shot uptake, and (2) a flu shot timing analysis, but also testing for main effects of a binary message-timing predictor variable (early or late) and interactions between message type and timing.

Analysis exclusion criteria

The following groups of patients will be excluded from all analyses:

Contraindicated patients: We unintentionally failed to remove a small number of patients contraindicated for flu vaccines from the sample prior to sending letters. After the error was discovered (after letters were sent, but prior to myGeisinger or SMS messages), because this was an exclusion criterion for the study, we removed the patients completely from the study, including from all analyses.

Patients deceased prior to our study start date (9/9/21): Midway through the study, we received an updated list of patients who were deceased. Some had died prior to the study beginning but medical records had not yet been updated to reflect the date of death. These patients will be removed from all analyses.

The following groups of patients will be excluded from all analyses, except the intent-to-treat analysis (robustness analysis) as described above:

Patients deceased during the study: A very small number of patients were recorded as deceased between the date we originally pulled the data and the date of the updated pull. These patients will be removed from analyses.

Patients sent protective risk reasons: Additionally, in determining the reasons each person was considered high risk, we unintentionally included reasons that were negatively weighted for a small number of patients. That is, for these patients, one or two of the reasons listed for their high-risk determination were *protective* against flu, despite their overall high-risk designation by the model. These patients will be removed because their messages may have been confusing and were not the precise messages we originally intended to send. For consistency across groups, we will also remove those in groups who were not sent reasons, but who would have received protective risk reasons had reasons been included in their messages.

Patients vaccinated prior to the study beginning: Area pharmacies and some Geisinger clinics began offering flu vaccines prior to our study beginning. We will remove patients from analysis who received a flu shot prior to 9/9/21, the study start date.

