After the intervention is complete, we will obtain experimental outcome data for all 3 population groups from BIAA & PACDC. This will include data on patient flu vaccination, diagnosis of flu, diagnosis of flu-like symptoms, presence of flu-associated complications, hospital visits,

emergency department visits, and covid vaccination status. This data set will additionally include patient characteristics that will be useful as analysis covariates, such as: age, patient primary care provider, and flu-related behavior and outcomes during previous flu seasons.

STUDY DATA DETAILS

Data Management Procedures and Confidentiality. All data will be electronic. Datasets with full identifying information will only be stored on Geisinger-managed, password-protected computers of the data brokers ([name] and [name]) for the purpose of linking datasets from different sources.

A limited data set containing dates of service and ZIP codes will be shared with any non-Geisinger collaborators (e.g., Additional Principal Investigator [name] and his team) under a Data Use Agreement (pending approval) in compliance with HIPAA's Privacy Rule, and using data security protocols reviewed and approved by the Geisinger Security Office, Privacy Office, and Information Technology department.

After all data have been linked in a de-identified, coded file and analyzed, the datasets with identifiable information and any codes needed to link the identifiable information will be deleted. After the de-identified data have been fully analyzed, the de-identified dataset will be shared along with publications from this study. The deidentified data will not be destroyed or removed after any prespecified period of time has elapsed. We intend to permanently and securely archive the deidentified dataset at a research repository such as Open Science Framework (OSF) in order to be consistent with the best practices for open and reproducible science, as well as our obligation to the public as NIA-funded researchers.

The only study team members who will have access to fully identifiable and protected health information will be [name] and [name]. Non-Geisinger collaborators will have access to a limited data set containing dates of service and ZIP codes. The remaining investigators will have access to the de-identified, coded data during data analysis.

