Using Explainable AI Risk Predictions to Nudge Influenza Vaccine Uptake

NCT05009251

11/10/2021

Protocol and Statistical Analysis Plan

Brief Summary

The study team previously demonstrated that patients are more likely to receive flu vaccine after learning that they are at high risk for flu complications. Building on this past work, the present study will explore whether providing reasons that patients are considered high risk for flu complications (a) further increases the likelihood they will receive flu vaccine and (b) decreases the likelihood that they receive diagnoses of flu and/or flu-like symptoms in the ensuing flu season. It will also examine whether informing patients that their high-risk status was determined by analyzing their medical records or by an artificial intelligence (AI) / machine-learning (ML) algorithm analyzing their medical records will affect the likelihood of receiving the flu vaccine or diagnoses of flu and/or flu-like symptoms.

Power analysis

The study team planned to enroll about 9400 patients per group, and a total of 47,000 patients across all 5 groups in the study. Assuming a baseline vaccination rate of 40% (based on baseline vaccination rate from our previous study), this sample would allow 80% power to detect 2% absolute difference, or a 5% relative difference, between two groups.

Sample and Randomization

The sample was slightly smaller than planned, with 45,164 patients total in the top 10% of risk for flu and flu-related complications among Geisinger patients who were over age 18.

The sample was first divided into those in the top 3% and those in the next lower 7% of risk (henceforth “top 10%”, the label used when subjects are contacted). Each of those groups (top 3%, top 10%) were randomized into one of 5 groups:

1. No-contact control - no messages were sent
2. Reminder control - message(s) encouraging the patient to get a flu shot but not mentioning anything about risk
3. High Risk Only - message(s) disclosing the patient's *high-risk status*, with no information about how their risk status was determined
4. High Risk with Explanation Based on Medical Records - message(s) disclosing the patient's *high-risk status* with the added explanation that they are at high risk based on a *review of their medical records* and with the top *reason(s) why they are considered high risk*

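### Flu diagnosis is detected only through contact with care, and Analyses 1a and 1b compare warned with unwarned patients on it without any check on flu testing by arm

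*SAP*

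**What the plan says.** The SAP's Brief Summary asks whether giving reasons for high-risk status "decreases the likelihood that they receive diagnoses of flu and/or flu-like symptoms in the ensuing flu season". Under Secondary outcomes, item 2 defines flu diagnosis in two tiers: a high-confidence tier that needs a positive test, and a likely-flu tier "as assessed via International Classification of Disease [ICD] codes or Tamiflu administration or positive PCR/antigen/molecular test". On analysis it says "We will use the approaches described in analyses 1-4 above to evaluate the impact of the intervention on the secondary outcome measures".

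Analysis 1a compares groups 3-5 (risk disclosed) with group 2 (reminder without risk). Analysis 1b compares groups 3-5 with group 1 (no contact). Outcomes come from health-system records (Protocol, Data Sources), and no scheduled testing or active surveillance is described.

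The sensitivity and robustness checks cover shared addresses, logistic models, exclusions, a Geisinger PCP, and age and sex. The PCP check is justified only by the reliability of flu-shot records. Item 4 of the secondary outcomes covers ER visits, hospitalisation and flu-related claims, but is not linked to how flu is detected.

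The Protocol's extraction list includes "diagnosis of flu-like symptoms". The SAP's list of secondary outcomes has no such item.

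**The concern.** A patient told of a high risk of flu complications may be quicker, or slower, to attend with a cough, to be tested or to be treated. If so, the arm difference in diagnosed flu in 1a and 1b combines two things: infections prevented by extra vaccination, and a change in the share of infections that are recorded. Randomisation does not separate them, because the second is also caused by the message. Restricting to the high-confidence tier does not remove the problem, since a test must still be taken.

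At stake is how 1a and 1b are read on this outcome. A null or reversed estimate could be taken to mean that risk messages do not reduce flu, when part of it reflects detection. A favourable estimate could likewise reflect reduced detection. The plan collects nothing on flu testing that would let a reader judge.

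**Working it through.** **Inputs from the documents.** About 9,400 patients per group planned, 40% baseline uptake, and the statement that "this sample would allow 80% power to detect 2% absolute difference, or a 5% relative difference, between two groups" (SAP, Power analysis). Actual sample: "45,164 patients total in the top 10% of risk" (SAP, Sample and Randomization). With equal allocation, 45,164/5 ≈ 9,033 per group and about 27,098 in groups 3-5, before exclusions. The Protocol's Background gives an 8% seasonal flu rate for the US population.

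**Assumptions not in the documents.** Vaccine effectiveness (VE): 40-60%, with 10-70% shown. Two-sided alpha of 0.05. Diagnosed-flu rate in this sample: 8%, with 2% as a lower case. The effect of a warning on detection is unknown.

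**1. The plan's own figure.** 40% v 42% with 9,400 per group: null SE = √(2 × 0.41 × 0.59/9,400) = 0.00717, and the SE under the alternative is also 0.00717. Power = Φ((0.02 − 1.96 × 0.00717)/0.00717) = 79.6%, so the stated 80% reproduces. At 9,033 per group it is 78.0%.

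**2. Vaccine-mediated fall and the detection rise that offsets it.** With flu risk proportional to 1 − VE × uptake, RR = (1 − 0.42 VE)/(1 − 0.40 VE), and the offsetting relative rise in detection is 1/RR − 1.

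- VE 40%: RR = 0.832/0.840 = 0.9905.
- VE 60%: RR = 0.748/0.760 = 0.9842.

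| VE | Fall in flu | Offsetting rise |
|---|---|---|
| 10% | 0.21% | 0.21% |
| 20% | 0.43% | 0.44% |
| 30% | 0.68% | 0.69% |
| 40% | 0.95% | 0.96% |
| 50% | 1.25% | 1.27% |
| 60% | 1.58% | 1.60% |
| 70% | 1.94% | 1.98% |

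The offset moves roughly in proportion to the uptake gain. At VE 40-60% it is 0.48-0.80% for a 1-point gain and 1.45-2.43% for a 3-point gain.

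**3. Sampling noise in 1b.** At an 8% diagnosed rate, SE = √(0.08 × 0.92 × (1/27,098 + 1/9,033)) = 0.0033, or 0.33 points (4.1% relative). The true fall is 8% × 0.95% to 8% × 1.58%, or 0.08-0.13 points, so power for it is about 6-7% with no detection bias at all. At a 2% rate the relative SE is 8.5% and power is about 5%. Analysis 1a has the same group sizes.

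**4. Rise needed for a significant false harm in 1b.** Solve RR × (1 + rise) = 1 + 1.96 × relative SE. At an 8% rate, 1.0808/0.9905 − 1 = 9.1% and 1.0808/0.9842 − 1 = 9.8%. At a 2% rate it is about 18%. A 3% rise gives 0.9905 × 1.03 = 1.020 or 0.9842 × 1.03 = 1.014, a net +1.4% to +2.0%, which is under half a standard error.

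**5. What a test-based check could see.** If 10% of patients had the tested outcome (an assumption), its relative SE would be √((0.9/0.1) × (1/27,098 + 1/9,033)) = 3.6%, so the 95% interval would reach about ±7%. That is informative about shifts near 9-10%, but not about 1-1.6%.

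**The case against.** The strongest reply has four parts.

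- **The reasons question is not a warned-against-unwarned comparison.** The Brief Summary's question about reasons is answered by groups 4-5 against group 3, and its question about records or algorithm by group 4 against group 5. All these arms are told they are at high risk. This stands. A reader might infer that the whole flu objective is undermined, but the documents do not support that. Analyses 2 and 4 are much less exposed, though not immune, since groups 4 and 5 also receive personal risk factors that group 3 does not.
- **The plan speaks of diagnoses, not infections.** That is largely so, and the remedy is partly to hold the report to that wording.
- **Attendance is already measured.** ER visits, hospitalisation and claims are compared by arm, so it would be wrong to say that nothing on care contact is planned. But this outcome omits outpatient contact and flu testing. The Protocol also expects claims for only about 40% of participants.
- **Imprecision dominates.** This stands too. With 6-7% power, a null is likely with or without differential detection. A reader might infer that a small rise in care-seeking would make an effective message look harmful. Step 4 shows that a 3% rise would be indistinguishable from chance.

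Nor do the documents show that a warning raises care-seeking. It is plausible, because the trial's premise is that disclosing risk changes health behaviour, but no figure or direction is given. Some flu will also be found by tests during admissions for other reasons, so the dependence is on contact with care rather than on a choice to attend.

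**Conclusion.** The concern holds in a limited form. Flu diagnosis depends on contact with care in every component, 1a and 1b compare warned with unwarned arms, and no planned analysis measures flu testing by arm. Under a 2-point uptake gain and VE of 40-60%, a detection rise of 0.96-1.60% would offset the expected vaccine effect (0.21-1.98% over VE 10-70%). These figures are conditional: VE is an outside assumption, and the 2 points is the difference the trial was sized to detect, not a forecast. They describe a shift in the expected estimate within sampling noise. A significant false harm would take a rise of about 9-10% at an 8% diagnosed rate.

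This affects the interpretation of one secondary outcome in two contrasts. It does not affect the primary vaccination outcome. The missing flu-like-symptom outcome is a separate mismatch between the objective and the outcome list, and is not evidence of detection bias. The change is cheap and worth making. The SAP's Project status section says that no outcome data had been extracted, so it could be specified without sight of results.

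**What to change.** From the same EHR extraction, and with the 1a and 1b contrasts:

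1. Analyse negative flu PCR/antigen/molecular tests by arm as a negative-control outcome. Flu vaccination should not lower these, so a difference points to testing behaviour.
2. Analyse any flu test by arm, whatever the result. Read it beside item 1, because total tests also fall if vaccination prevents illness.
3. Report both as differences with confidence intervals. Do not use non-significance as a pass mark: step 5 shows that such a test could not exclude a 1-1.6% shift.
4. State that 1a and 1b on this outcome estimate effects on diagnosed flu, and are read as effects on flu itself only in the light of those intervals.
5. Show hospitalisation with positive-test flu as a supportive measure, with all randomised patients as the denominator. Conditioning on admission would select on a post-randomisation event.

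Separately, add flu-like-symptom diagnosis as an outcome in its own right. It should not serve as a negative control, because it includes untested true flu, which vaccination should lower.

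The cost is pulling negative results with the positive ones, a few extra regressions and an interpretation sentence. The downside is a weaker claim if testing differs by arm, and wide intervals, most of all for hospitalised flu.

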Because this intervention is timed to the 2021–22 flu season, the intervention period will begin ~9/1/21. Subjects in treatment Arms #2–5 will receive the same type of communication via up to three modalities—printed letters to their mailing addresses, SMS to their mobile phones, and/or secure messages via Geisinger’s patient portal—depending on what consent and information is on file for each patient. Messages will be staggered by modality, starting with postal letters, then sending the same message via the patient portal two weeks later, and a final message via SMS after four weeks.

The primary outcome will be whether the patient was vaccinated during the first six weeks after the intervention begins. A secondary outcome will be vaccination within three months after the intervention begins. Additional secondary outcomes to be measured through the end of the flu season (start of intervention through 3/31/22) will include: rates of flu diagnoses (both using the most rigorous biological tests, “high confidence flu”, and using broader criteria that also include diagnosis codes and treatment information, “likely flu”), flu complications, and rates of other relevant healthcare utilization outcomes such as ER visits, hospitalizations, insurance claims (for an expected ~40% of participants who are members of Geisinger Health Plan) by patients, household members of patients, and those at sub-threshold risk. We will also measure rates of flu vaccination by fellow household members of targeted patients and non-targeted patients at sub-threshold risk. Finally, we will measure rates of COVID-19 vaccination in targeted patients, household members, and those at sub-threshold risk.

Data Sources

In order to identify patients in the primary target population, **Business Intelligence & Advanced Analytics** (BIAA), working with **Geisinger’s Phenomics and Clinical Data Core** (PACDC), will provide a list of patients (including patient identifiers such as Medical Record Number) that were assessed by the Medial and each patient’s associated risks.

We will also obtain contact information (address, phone number, email address) to message participants in the primary target population from BIAA & PACDC.

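### The exploratory modality contrasts carry any baseline uptake gap between eligibility classes one for one; adding covariates and a complementary comparison with the no-contact group would be a cheap improvement

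*SAP*

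**What the plan says.** Item 3 (Modality) of the SAP's additional exploratory analyses takes the patients in groups 2 to 5 and says: "We will employ OLS regression to evaluate the impact of modality on outcomes of interest, assessing pairwise comparisons of the following modality combinations". Four combinations follow: letter alone, letter with portal message, letter with SMS, and all three. No covariate and no comparison with group 1 is named. The SAP adds that the number of modalities was not randomised but "determined by patient preferences and data availability in the EHR, so these are observational analyses only". The protocol's Detailed Study Procedures agree: modality varied "depending on what consent and information is on file for each patient".

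Four other places bear on the point.

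- **No-contact group.** Under Sample and Randomization, two risk strata are defined and "Each of those groups (top 3%, top 10%) were randomized into one of 5 groups". One of the five is the no-contact control.
- **Covariates.** The protocol's Data Sources section plans to obtain characteristics "useful as analysis covariates, such as: age, patient primary care provider, and flu-related behavior and outcomes during previous flu seasons".
- **Adjusted reruns.** Among the robustness checks, which precede the exploratory section, the SAP says "we will run OLS regression analyses controlling for sex, 10-year age bins, and interactions among sex and age as covariates". It also plans a rerun with an indicator for a Geisinger primary care provider. It does not say whether either rerun extends to the modality analysis.
- **Interaction with arm.** Item 2 (Age) of the exploratory analyses enters age as a moderator, "assessing if it interacts with experimental group to affect vaccination behavior".

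**The concern.** Patients who have given SMS consent or use the portal may differ from letter-only patients in how likely they are to be vaccinated, or to have a shot recorded, without any message. A contrast confined to messaged patients cannot separate that difference from an effect of the extra messages. Labelling the result observational tells the reader to be careful but leaves the gap in the estimate, and the stated aim is still the impact of modality.

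The trial has two resources that could reduce the gap, and this item uses neither: covariates it already plans to obtain, and a randomised group that was sent nothing. At stake is how an exploratory table is read. A health system choosing channels could take a difference in who is reachable for a difference in what the channel does.

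**Working it through.** **Inputs from the SAP.** The sample is 45,164 in five groups. Equal allocation is assumed, as the planned 9,400 per group and 47,000 in total imply, so n = 45,164/5 = 9,033 per arm and 4n = 36,131 in groups 2 to 5, before the analysis exclusions. The baseline rate is 40%, so the variance per patient is 0.4 × 0.6 = 0.24.

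**Assumed.** The documents give no class shares, no uptake by eligibility and no significance level. I take two-sided 5%, and two classes each holding a share s of patients.

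**The plan's own figure.** 9,400 per group, 40% against 42%, gives 79.6% power, which matches the stated 80%. The SAP gives no figure for the modality analysis.

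**What each contrast estimates.** For eligibility classes A and B:

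- Planned, groups 2 to 5: (baseline A − baseline B) + (message effect A − message effect B).
- Arm × class, groups 2 to 5 against group 1: (message effect A − message effect B). Group 1 is randomised, so subtracting its class difference removes the first term in expectation.

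The second term contains both modality and any difference in how the classes respond to messages of any kind. Neither contrast separates those two.

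**Standard errors (percentage points).**

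- Planned: sqrt(2 × 0.24/(4n·s)).
- Message effect within one class: sqrt(0.24/(4n·s) + 0.24/(n·s)).
- Between-class difference of those effects: the within-class value × sqrt(2).
- The ratio of the last to the first is sqrt(5) = 2.24 for any s.
- Detectable at 80% power: 2.80 × SE.

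| Share s of each class | Planned SE | Within-class SE | Between-class SE | Detectable, between-class |
|---|---|---|---|---|
| 15% | 0.94 | 1.49 | 2.10 | 5.9 |
| 25% | 0.73 | 1.15 | 1.63 | 4.6 |
| 40% | 0.58 | 0.91 | 1.29 | 3.6 |

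Classes of 15% and 40% give a between-class SE of 1.74 and 4.9 points detectable. If exclusions remove 20% of patients, two 25% classes give 1.82 and 5.1.

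**Chance of a significant result with no modality effect, s = 25%.**

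| Difference (points) | Planned, baseline gap only | Arm × class, responsiveness difference only |
|---|---|---|
| 0.5 | 11% | – |
| 1 | 28% | 9% |
| 2 | 78% | 23% |
| 5 | nearly 100% | 87% |

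With a baseline gap and equal responsiveness, the arm × class contrast stays at 5%. For classes of 5% and 60%, the planned contrast rejects in 13%, 39% and 99% of trials at gaps of 1, 2 and 5 points.

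**Simulation (40,000 runs per case, s = 25%).** With equal responsiveness and gaps from −5 to 5 points, the arm × class contrast rejected in about 5% of runs and averaged within 0.02 points of zero. With a gap of −2 and a responsiveness difference of +2, the planned contrast rejected in 5% of runs because the two terms cancel. The arm × class contrast rejected in about 23%.

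**Total error.** With equal responsiveness, the planned contrast has root-mean-square error sqrt(0.73² + gap²), against 1.63 for arm × class. They are equal at a gap of sqrt(1.63² − 0.73²) = 1.46 points. Below about 1.5 points the planned contrast is closer to the truth on average. The crossing point is 1.9 for two 15% classes and 1.2 for two 40% classes.

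**The case against.** The strongest reply is that the SAP already says this. It states that modality was not randomised, places the analysis among the exploratory ones and limits its interpretation. That stands: nothing is concealed and nothing is contradictory. What remains is that the disclosed weakness could be reduced with data the trial expects to hold.

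Second, no gap has been demonstrated. That also stands. A reader might infer from the 78% figure that the modality result will be spurious. The documents do not support that, because the figure shows only what an assumed 2-point gap would do in a sample of this size.

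Third, silence on covariates is not a decision to omit them. The protocol's general analysis paragraph allows predictors in regression models, and the robustness reruns might be meant to extend here. So one for one is exact only for the unadjusted contrast. With covariates, the residual gap would enter.

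Fourth, the arm × class contrast does not deliver a modality effect and can be the worse estimate, either when the gap is small or when gap and responsiveness differ in sign. This stands in full. A reader might infer that it should replace the planned contrast or become the main exploratory result. Its precision and its remaining mixture with responsiveness argue against both.

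Fifth, eligibility for group 1 may not be retrievable. The protocol's on-file wording concerns arms 2 to 5. Retrieval is plausible: contact data are to be obtained for the primary target population, the shared-address sensitivity analysis needs addresses, and the SAP already classifies patients not sent reasons by the reasons they would have received. None of this establishes that portal and SMS fields were kept as of randomisation.

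**Conclusion.** This is a minor point, confined to one exploratory analysis. As written, the modality contrasts carry any baseline uptake difference between eligibility classes at full size, and the item names none of the available means of reducing it. Whether such a difference exists, and its size and direction, cannot be learned from the documents. Every rejection rate and standard error above rests on equal allocation, 40% uptake and assumed class shares.

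The comparison with group 1 removes the baseline part only. Its real gain is a randomised message effect within each eligibility class, which the planned model does not provide. For two 25% classes, the between-class comparison of those effects can detect about 4.6 points and has about 23% power for a true 2-point difference. The two contrasts therefore complement each other.

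A reader might go further and infer that the trial's main conclusions are exposed. They are not: Analyses 1 to 3 compare randomised groups and do not condition on modality.

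**What to change.** 1. Keep the planned contrast. Report it unadjusted and also with age, prior-season flu vaccination and risk stratum (top 3%, next 7%) as covariates. This addresses only the part of a gap that those variables explain.
2. As a complementary analysis, classify all five groups by modality eligibility on file at randomisation, if the fields can be retrieved for group 1. Fit arm (groups 2 to 5 against group 1) × eligibility class, with risk stratum as a covariate. Report the message effect within each class with its interval. The form resembles the SAP's age-moderator analysis, with the four messaged arms pooled.
3. Classify by eligibility, not by what was sent. Portal and SMS messages were withheld from "patients who were never sent a letter, or whose mail was returned prior to these modality send dates", and returned mail cannot be observed in group 1. Portal- or SMS-eligible patients with returned mail then stay in their class. Patients with no valid address are reported separately. The SAP calls these patients a small group.
4. State that between-class differences in the message effects remove only the baseline gap and still mix modality with responsiveness. Present both contrasts side by side and label neither as the main one.

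The cost is a few sentences in the SAP, one interaction model, and address, portal and SMS-consent fields for group 1. The SAP reports that no outcome data had been extracted or analysed at its date, so the addition could be prespecified at that stage. The downside is the 2.24-fold larger standard error of the between-class contrast. If the group 1 fields cannot be obtained, step 1 alone is still worth doing.
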